2.8.4.2 Vital signs

The number and percentage of subjects with clinically notable vital signs will be presented. The same approach as for notable laboratory values will be used to define newly occurring notable vital sign values. Notable vital sign values will be listed.

Notable criteria are:

Variable	Criterion value		Change relative to baseline
Heart rate/pulse	120 bpm 50 bpm	and an and a	increase of ≥ 15 bpm decrease of ≥ 15 bpm
Systolic blood pressure	180 mm Hg 90 mm Hg	and an and a	increase of ≥ 20 mm Hg decrease of ≥ 20 mm Hg
Diastolic blood pressure	105 mm Hg 50 mm Hg	and an and a	increase of ≥ 15 mm Hg decrease of ≥ 15 mm Hg
Weight	Baseline weight (kg)	and an and a	increase of ≥ 7% decrease of ≥ 7%

bpm= beats per minute

Data of subjects with newly occurring notable vital signs abnormalities will be listed in an additional listing.

2.8.4.3 Physical examination

Physical examination including examination of skin will be source documentation only.

2.9 Pharmacokinetic endpoints

Scatter plots of EMA401 plasma concentrations will be displayed in linear and semilogarithmic view in a CSR addendum.

2.10 PD and PK/PD analyses

Evaluation of effect of EMA401 exposure on efficacy variables (e.g. change from baseline of pain score), via the development of a continuous descriptive Pharmacokinetics/ Pharmacodynamics (PK/PD) was planned in the protocol. All population PK/PD analyses and simulations were to be carried out using a non-linear mixed-effects modelling approach. Due to early study termination the planned model based exposure-response analysis will not be performed and replaced with a graphical assessment of the exposure-response relationship.

This will be reported in a separate report.

2.11 Patient-reported outcomes

Please refer to efficacy analysis for details on all Patient Reported Outcomes (PRO).

2.12 Biomarkers

Not applicable.

2.13 Other Exploratory analyses

The following exploratory analysis will be performed:

1. The proportion of patients who need rescue medication (at each visit and at least once during the study) will be evaluated. The corresponding binary variables will be derived and analyzed based on a logistic regression model with the same factors as the ANCOVA model for the primary analysis.
2. The Kaplan-Meier estimates of the proportion of patients with rescue medication intake, along with the associated 95% confidence intervals using the Greenwood's formula will be provided.
3. The proportion of EMA401 patients achieving a 30%, 50% reduction in the weekly mean of the 24-hour average NRS pain score compared to placebo at Week 4 and at Week 12 will be evaluated after multiple imputation is done on the primary variable. The corresponding responder variables will be derived and analyzed based on a logistic

regression model with the same factors as the ANCOVA model for the primary analysis. Cumulative responder plots will be displayed.

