9.6 Analysis of exploratory variables

The following exploratory analysis will be performed:

4. The proportion of patients who need rescue medication (at each visit and at least once during the study) will be evaluated. The corresponding binary variables will be derived and analyzed based on a logistic regression model with the same factors as the ANCOVA model for the primary analysis.
5. The time to first rescue medication intake will be compared between each dose of EMA401 and placebo via a Cox proportional hazard regression model with the same set of covariates used for the primary analysis. The corresponding hazard ratio with the 95% confidence interval will be reported. The Kaplan-Meier estimates of the proportion of patients with rescue medication intake, along with the associated 95% confidence intervals using the Greenwood's formula will be provided.

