DMC	Data Monitoring Committee
ECG	Electrocardiogram
eCRF	Electronic Case Report Form
ED ₅₀	The dose at which half of the maximum effect is reached
eGFR	Estimated Glomerular Filtration Rate
E _{max}	The maximum effect attributable to the drug
FAS	Full Analysis Set
FDA	Food and Drug Administration
GGT	gamma-glutamyltransferase
HIV	Human Immunodeficiency Virus
INR	International Normalized Ratio
IRT	Interactive Response Technology
ISI	Insomnia Severity Index
LFT	Liver function test
LoE	Lack of efficacy
MAR	Missing at random
mFAS	Modified Full Analysis Set
MCP-Mod	Multiple Comparison Procedure – Modelling
MDRD	Modification of Diet in Renal Disease
MedDRA	Medical dictionary for regulatory activities
NPSI	Neuropathic Pain Symptom Inventory
NRS	Numeric Rating Scale
NSAID	Nonsteroidal Anti-inflammatory Drugs
PCR	Protein-Creatinine Ratio

PHN	Post-Herpetic Neuralgia
PK	Pharmacokinetics
PGIC	Patient Global Impression of Change
PRO	Patient Reported Outcome
█	█
QTc	Corrected QT interval
QTcB	Bazett QT correction formula
QTcF	Fridericia QT correction formula
SAE	Serious Adverse Event
RDO	Retrieved drop-out
SAF	Safety population
█	█
SSRI	Selective Serotonin Reuptake Inhibitor
TBL	Total bilirubin
TD	Study Treatment Discontinuation
TEAE	Treatment-Emergent Adverse Events
ULN	Upper limit of Normal
USM	Urgent Safety Measures
VRS	Verbal Rating Scale
WHO	World Health Organization

Amendment 1

This amendment of the statistical analysis plan (SAP) is largely based on changes induced due to the early termination of the CEMA401A2201 study. 129 patients out of 360 planned patients have been randomized. As the number of patients included in the study is considerably reduced, an abbreviated Clinical Study Report (CSR) that still meets all requirements for reporting and disclosure of the demographics, primary endpoint, secondary endpoints and safety results to public registries will be created.

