The primary analysis on the change from baseline to Week 12 in the weekly mean of the 24-hour average pain score will be performed as originally planned. Besides the primary estimand, which is of main clinical interest, the supplementary estimand, which provides insight into the magnitude of improvement in efficacy that might be achieved if all patients were able to take EMA401 as prescribed for 12 weeks, will be analysed. The other planned supplementary estimands will be dropped, as they are of minor interest in the situation with many study treatment discontinuations due to trial termination in the scope of the Urgent Safety Measures (USM).

To support the primary analysis and to get an idea about the effect that might be achieved if the trial had not been terminated and if all patients had the chance to complete the Week 12 assessment, a sensitivity analysis on a modified population will be performed. The modified full analysis set will include all patients who had a chance to complete the study before the termination date, i.e. who had been randomized at least 12 weeks before study termination date.

Due to the considerably reduced number of patients who completed the study, only descriptive subgroup analyses will be provided. Moreover, most of the secondary [REDACTED] endpoints will also be summarized descriptively only. [REDACTED]

1 Introduction

This statistical analysis plan (SAP) describes all planned analyses for the Clinical Study Report (CSR) of study CEMA401A2201, a Phase 2, double-blind, placebo-controlled, randomized dose ranging trial to determine the safety and efficacy of three dose levels of EMA401 in reducing 24-hour average pain intensity score in patients with post-herpetic neuralgia.

The content of this SAP is based on the final version of protocol CEMA401A2201 Amendment 1 (release date 14-May-2018). All decisions regarding final analysis, as defined in the SAP document, have been made prior to database lock and unblinding of the study data.

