2.4.2.1 Rescue medication

The number and percentage of patients who received rescue medication (Acetaminophen/Paracetamol as reported on the diary page) will also be summarized by treatment and by visit during the double blind and treatment withdrawal period separately. Visit mapping will be done according to the visit window strategy document. The dose received will be listed.

Analysis of time to first use of rescue medication will be performed using Kaplan-Meier curves. Number of patients with at least one intake will also be summarized.

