The planned sample size allows to estimate the placebo-corrected response (the treatment difference between the active EMA401 doses and placebo) with a root mean squared error of 0.34 averaged over the three active doses and taking the maximum over the 5 candidate models.

4 Change to protocol specified analyses

An additional population, the mFAS population, has been defined.

The following analyses were specified in the protocol but will not be performed due the early termination of study:

- first and third supplementary analysis to the primary analysis
- tipping point analysis
- supplementary responder analyses
- ANCOVA analyses for BPI-SF, worst NRS pain score, ISI
- Proportional odds model for PGIC
- Apart from analyses of clinical abnormalities summaries of laboratory data, vital signs and ECG intervals have been removed.
- Shift tables of laboratory data
- No safety figures will be presented
- Bazett correction for QTc
- time to "sustained" pain reduction

The following analyses have been added:

- sensitivity analyses on modified full analysis population
- analyses of TEAEs with onset before study termination date

The analyses of patient disposition for the treatment and treatment withdrawal epoch will be based on the FAS population only.

Analyses of duration of exposure to study treatment will be based on the SAF population only.

5 Appendix

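### The retained logistic regression of ever using rescue medication ignores time observed, and the protocol's Cox comparison is gone without an entry in SAP Section 4

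*SAP*

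**What the plan says.** Protocol 9.6 plans two between-arm analyses of rescue use. One is a logistic regression of the proportion needing rescue, by visit and over the whole study. The other is a time-to-event comparison: "The time to first rescue medication intake will be compared between each dose of EMA401 and placebo via a Cox proportional hazard regression model". That model uses the primary analysis covariates and reports a hazard ratio with 95% confidence interval; Kaplan-Meier estimates accompany it.

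SAP 2.13 repeats the first analysis: "The proportion of patients who need rescue medication (at each visit and at least once during the study) will be evaluated", and "The corresponding binary variables will be derived and analyzed based on a logistic regression model with the same factors as the ANCOVA model". Of the second it keeps only "The Kaplan-Meier estimates of the proportion of patients with rescue medication intake", with Greenwood intervals. SAP 2.4.2.1 adds: "Analysis of time to first use of rescue medication will be performed using Kaplan-Meier curves". The readable SAP contains no Cox model, hazard ratio or log-rank test for rescue use.

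SAP Section 4 opens its list of omissions with "The following analyses were specified in the protocol but will not be performed due the early termination of study". The list has ten entries and shows no redaction. The rescue Cox model is not among them. Time to first rescue intake is still an exploratory objective in SAP Table 1-1.

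The Amendment 1 rationale in the SAP records that "129 patients out of 360 planned patients have been randomized" and that many treatment discontinuations came from the termination.

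**The concern.** A patient observed for one week without rescue counts as a non-user, exactly like a patient observed for twelve weeks without rescue. When everyone is followed for the same period this does no harm. Here the trial was cut off on one calendar date. SAP 2.2 defines the modified full analysis set by randomization at least 12 weeks before 25 February 2019, so anyone randomized after 3 December 2018 could not reach Week 12. Patients also stopped for other reasons. SAP 2.13 gives the ever-use model no offset, fixed window or minimum observation time, and SAP 2.5.4.2 applies the modified set only to the primary ANCOVA.

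The plan therefore keeps the model that ignores observation time and leaves out the between-arm model that allows for it. At stake is the ever-use odds ratio, which could partly reflect a difference in diary time instead of a difference in need for rescue.

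**Working it through.** **Plan's own figure.** The documents give none for rescue use. Their one power figure, at least 77% for the primary dose-response test, reproduces (minimum 0.771 over the five candidate shapes) but has no bearing here.

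**Inputs.** The documents give no rescue rate and no stop rate by arm, so the following are assumptions:
- a constant rescue hazard *h* of 0.03, 0.06 or 0.12 per week, the same in both arms (no true effect);
- a fraction *p* of patients stop at Week 3 for reasons unrelated to rescue and make no diary entries afterwards; the rest are observed for 12 weeks;
- *p* = 10% in placebo, and 20% or 25% in an active arm.

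**Formulas.**
P(ever) = (1 − p)(1 − e^(−12h)) + p(1 − e^(−3h))
OR = [P_active/(1 − P_active)] / [P_placebo/(1 − P_placebo)]

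**Worked case, h = 0.06.** 1 − e^(−0.72) = 0.5132 and 1 − e^(−0.18) = 0.1647.
Placebo: 0.90 × 0.5132 + 0.10 × 0.1647 = 0.478.
Active, 25% stops: 0.75 × 0.5132 + 0.25 × 0.1647 = 0.426.
OR = (0.426/0.574)/(0.478/0.522) = 0.81.

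| h per week | Placebo P | Active P, 25% stops | OR | Active P, 20% stops | OR |
|---|---|---|---|---|---|
| 0.03 | 0.281 | 0.248 | 0.846 | 0.259 | 0.896 |
| 0.06 | 0.478 | 0.426 | 0.810 | 0.443 | 0.869 |
| 0.12 | 0.717 | 0.648 | 0.726 | 0.671 | 0.805 |

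The true odds ratio is 1 in every row.

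**What changes the result.**
- *Equal stops in both arms:* the two probabilities coincide and the OR is 1.00.
- *Half of the stoppers keep the diary:* the effective fractions become 5% and 12.5%, and the OR is 0.923, 0.901 and 0.841 for the three hazards. The bias is roughly halved.
- *A different stop pattern:* with stops spread evenly over 12 weeks and true 12-week rescue use of 30%, 50% or 70%, stops of 10% v 30% give ORs of 0.87, 0.84 and 0.78. Stops of 20% v 50% give 0.80, 0.76 and 0.70.
- *Stops that follow rescue use:* suppose every stopper has already taken rescue, other patients have 50% use, and stops are 10% v 30%. Ever-use is 0.90 × 0.5 + 0.10 = 0.55 v 0.70 × 0.5 + 0.30 = 0.65, so OR = (0.65/0.35)/(0.55/0.45) = 1.52. The arm with more stops now looks worse. By construction it also contains more rescue users, so this case shows that the sign cannot be presumed; it is not an equal and opposite artefact.

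**Test behaviour.** With 43 per arm (129/3), 8,000 simulated trials per setting, no true effect and evenly spread non-informative stops, an unadjusted ever-use test at the nominal two-sided 5% level rejected in 5.1% to 11.3% of trials when stops were unequal. It rejected in 4.2% to 4.7% when they were equal. The log-rank test, which is the Cox score test, stayed at 4.8% to 5.6% throughout. When stops followed rescue use, the log-rank test moved in the same direction as the odds ratio (mean z 1.09).

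**The case against.** A reader might infer that arms with more early stops will look better. The documents do not support that. They show no imbalance in stops or diary time. The termination date was common to all arms under 1:1:1 allocation, so the truncation it caused is expected to be balanced. Stopping treatment is not leaving the study: Protocol 5.6.2 encourages continued follow-up, Table 6-2 keeps the daily pain diary, and rescue for PHN pain is recorded in that diary. Stops for lack of efficacy may come after rescue and turn the direction round. These points stand and make the result conditional. They do not show that diary time is equal, and SAP 2.5.2 itself expects sparse data after treatment discontinuation.

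A reader might also infer that the Cox model was dropped without any notice. That goes beyond the readable text. The SAP amendment log names Section 2.13 as affected and is partly redacted. The rationale says, between redactions, that most secondary and other "endpoints will also be summarized descriptively only". SAP 5.5.3 has a heading but no readable content. What can be said is that the unredacted Section 4 list omits it.

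Two further points are fair. Kaplan-Meier estimates handle censoring and are kept, but as planned they give no adjusted contrast between arms. The logistic model was in the protocol from before termination, so it is not a new choice; what changed is that its time-to-event partner went.

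**Conclusion.** The point holds in conditional form, as a minor improvement. The ever-use odds ratio depends on observation time, observation time became unequal between patients, and the between-arm model that allowed for this no longer appears and is not listed in Section 4. If non-informative stops at Week 3 differ by 10 to 15 percentage points between arms with no diary afterwards, an odds ratio that should be 1 becomes about 0.73 to 0.90. That range rests wholly on assumed hazards and stop rates. Continued diary use moves it towards 1, and equal truncation removes it.

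Because the endpoint is exploratory, no primary or secondary conclusion is affected.

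**What to change.** Restore the Protocol 9.6 Cox model for time to first rescue intake in SAP 2.13: each dose against placebo, the same covariates as the primary analysis, censored at the last diary day, reported alongside the Kaplan-Meier estimates. Report the ever-use proportion descriptively only, and tabulate diary time by arm so that readers can judge whether it was balanced. If the sponsor prefers not to restore the model, add its removal to SAP Section 4 with the reason.

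The cost is one model that the protocol already specified. It assumes proportional hazards and non-informative censoring, and stops for adverse events or lack of efficacy may strain the second assumption. Both should be stated with the result.

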2.14 Interim analysis - Safety

The DMC is responsible for unblinded safety review to stagger patient exposure to the study drug. Randomization of patients to the high dose arm (EMA401 300 mg b.i.d.) will only be initiated following an unblinded safety review by an independent DMC after exposure of 50 patients treated with EMA401 up to 100 mg b.i.d. for at least 8 weeks (i.e. 25 patients on 25 mg b.i.d. and 25 patients on 100 mg b.i.d.). Furthermore, another unblinded safety review was planned after the completion of 12 weeks exposure of 30 patients in the EMA401 300 mg b.i.d. treatment arm to determine if 300 mg b.i.d. dosing can be continued as planned. Due to the early termination in the scope of USM the EMA401 300 mg b.i.d. treatment arm was not initiated as planned.

The DMC reviews cumulative safety data, including patient narratives for deaths, serious adverse events (SAEs), discontinuations due to adverse events and cases of interest (allergic dermatitis, and clinically significant abnormal hepatic and hematology values).

The details of the analysis required for DMC had been specified in a separate DMC analysis plan and not repeated here in detail.

3 Sample size calculation

With the planned sample size of $N=(90, 90, 90, 90)$ for placebo, 25 mg b.i.d., 100 mg b.i.d. and 300 mg b.i.d., the power of the dose-response trend test [to reject the null hypothesis of a flat dose-response curve where all dose means of EMA401 (EMA401 25 mg b.i.d., EMA401 100 mg b.i.d., EMA401 300 mg b.i.d.) are equal to the placebo mean] for the primary variable is at least 77% under the candidate models using the MCP-Mod methodology using $\alpha=0.025$ one-sided.

The power calculation is based on the following assumptions:

- The assumed true dose-response curves for power calculation are the 5 candidate shapes (see Section 2.5) with the model parameter chosen so that the maximum effect in the dose-range is 1.0 attained with the 300 mg b.i.d. dose.
- The standard deviation is 2.6 points (based on data from pregabalin historical trials – see FDA Approval Package Medical Review, 2004). In Study EMA401-003, a standard deviation of approximately 2.0 points was observed. A slightly higher value of 2.6 has been chosen to account for a possible higher variability due to a higher number of centers and due to multiple imputations (as opposed to single imputation) in the analysis.

The planned sample size allows to estimate the placebo-corrected response (the treatment difference between the active EMA401 doses and placebo) with a root mean squared error of 0.34 averaged over the three active doses and taking the maximum over the 5 candidate models.

4 Change to protocol specified analyses

An additional population, the mFAS population, has been defined.

The following analyses were specified in the protocol but will not be performed due the early termination of study:

- first and third supplementary analysis to the primary analysis
- tipping point analysis
- supplementary responder analyses
- ANCOVA analyses for BPI-SF, worst NRS pain score, ISI
- Proportional odds model for PGIC
- Apart from analyses of clinical abnormalities summaries of laboratory data, vital signs and ECG intervals have been removed.
- Shift tables of laboratory data
- No safety figures will be presented
- Bazett correction for QTc
- time to "sustained" pain reduction

The following analyses have been added:

- sensitivity analyses on modified full analysis population
- analyses of TEAEs with onset before study termination date

The analyses of patient disposition for the treatment and treatment withdrawal epoch will be based on the FAS population only.

Analyses of duration of exposure to study treatment will be based on the SAF population only.

5 Appendix

5.1 Imputation rules

5.1.1 Study drug

Missing/partial start date or end date of study treatment will not be imputed.

5.1.2 Diagnosis of PHN

Rules for imputing date of first diagnosis of PHN will be provided in Programming Dataset Specification (PDS) document in details.

5.1.3 AE date imputation

Rules for imputing AE end date or start date will be provided in Programming Dataset Specification (PDS) document in details.

5.1.4 Concomitant medication date imputation

Rules for imputing the CM end date or start date will be provided in Programming Dataset Specification (PDS) document in details.

5.1.5 Prohibited medication for PHN

Exclusion period of values in case of changed PHN medication or intake of prohibited medication will be derived as follows:

- Programming Dataset Specification (PDS) will describe how to identify dose changes of concomitant PHN medications and prohibited medications
- determine exclusion period: CM end date + x days where $x=3$ for changes in dose and $x=7$ for intake of prohibited medications with potential confounding effect
- if no medication end date available, then all values from medication start date onwards should be excluded

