5.5.7 Concomitant medication

The investigator must instruct the patient to notify the study site about any new medications he/she takes after the patient was enrolled into the study. All medications, procedures and significant non-drug therapies (including physical therapy and blood transfusions) administered after the patient was enrolled into the study must be recorded in the concomitant medications / significant non-drug therapies eCRF.

Each concomitant drug must be individually assessed against all exclusion criteria/prohibited medication. If in doubt the investigator should contact the Novartis medical monitor before randomizing a patient or allowing a new medication to be started.

Allowed concomitant medications can be initiated for patients if deemed necessary by the investigator, however they should be on stable dose at least 2 weeks (14 days) prior to V101 (i.e. Baseline visit).

1. Patients will be allowed to take **only one** of the following prescribed medications for managing their PHN, provided the dose level has been stable for at least 2 weeks prior to the Randomization Visit (Visit 101 i.e Baseline visit) and must remain at stable doses throughout the study (PRN (as needed) use is not allowed):
 - Pregabalin
 - Gabapentin
2. In addition to other medications for non-pain related co-morbid conditions, patients will be allowed to take throughout the study the following medications for other concomitant medical conditions. The dose level must be stable at Baseline and must continue at stable doses throughout the study (PRN (as needed) use is not allowed):
 - A benzodiazepine, zolpidem, diphenhydramine or related drugs for insomnia.
 - A selective serotonin reuptake inhibitor (SSRI) for depression.
 - Oral aspirin (≤ 325 mg/day) for cardio-protection.

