2.5.2 Statistical hypothesis, model, and method of analysis

The aim is to estimate the treatment effect of the investigational drug (EMA401) compared to placebo, for the target population on the primary pain parameter. The definition and the justification of the corresponding primary estimand, as well as the definition of the supplementary and secondary estimands are detailed in the Estimand Charter.

The primary estimation method is based on an Analysis of Covariance (ANCOVA) model including region (America or Europe and Australia, Asia), treatment, sex, use of concomitant pain medication for PHN (yes/no) as factors and age and baseline (mean pain intensity) score as covariate. The analysis will account for different intercurrent events (i.e. events that occur post-randomization) as follows:

- **Changes in doses of concomitant medication for PHN:** Efficacy observations collected during the period of changes in doses of concomitant medication for PHN (compared to baseline) and the 2-days thereafter will be excluded, since they are considered affected by the concomitant medication dose change. The resulting missing data after this step will be multiply imputed using the Missing at random (MAR) assumption.
- **Intake of rescue medication:** Efficacy data collected during intake of rescue medication will be used for analysis.

- **Intake of prohibited medications with potential confounding effect prior to study treatment discontinuation:** The prohibited medications with a potential confounding effect are defined as those listed in Table 2-1 requiring study treatment discontinuation. A list of prohibited medications is available at the following [REDACTED]

[REDACTED] Efficacy

observations collected during the intake period of such prohibited medications and the 7-days thereafter will be excluded, since they are considered affected by the prohibited medication intake. The resulting missing data after this step will be multiply imputed using the MAR assumption.

Table 2-1 Prohibited medication

Medication	Prohibition period	Action taken for study treatment
Prohibited prior to Randomization and throughout study		
High dose capsaicin patch (8%)	3 months prior to Randomization and after Randomization	Discontinue study treatment
Prohibited 2 week prior to Randomization and throughout the study		
Any skeletal muscle relaxant (e.g. baclofen, orphenadrine, methocarbamol)	2 weeks prior to Randomization and after Randomization	None

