Any change to a different standard of care medication from baseline (e.g. switch from pregabalin to gabapentin) will be treated as prohibited medication	After randomization	Discontinue study treatment

Retrieved drop-out (RDO) patients are defined as patients who discontinue study treatment and decide to remain in the study by following an abbreviated schedule of assessments. These patients must continue to adhere to protocol requirements (see respective protocol Table 6-2). The design feature of retrieved drop-outs, considered in order to minimize the occurrence of missing data on primary pain parameter, is exploited for the statistical analysis as follows:

- **Permanent discontinuation of study treatment due to AE, lack of efficacy (LoE) and use of prohibited medication:** If retrieved drop-out data are available, these will be used for analysis. If no data was retrieved after study treatment discontinuation, missing data

will be multiply imputed based on placebo arm data, i.e. “jump to reference” (J2R) assumption for the EMA401 arms, missing at random assumption for placebo arm (Carpenter, Roger, and Kenward 2013). If no RDO data was collected after study treatment permanent discontinuation, missing data will be multiply imputed based on the J2R assumption for the EMA arms and under the MAR assumption for placebo arm. Of note, alternatively one could build the imputation model based on the RDO data, however, we expect sparse RDO data which will likely hinder us to build an imputation model. More details on the imputation model are specified in Section 5.

- **Permanent discontinuation of study treatment due to other reasons than AE, LoE and use of prohibited medication (including discontinuation due to USM):** If efficacy data collected after study treatment discontinuation are available (retrieved drop-out), then the retrieved drop-out data will be excluded and missing data after study treatment discontinuation will be multiply imputed using the MAR assumption.

The multiple imputations will be carried out on the weekly mean pain score. Details on multiple imputation can be found in Section 5 of this document.

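### As written, the SAP's exclusion window for PHN medication changes closes three days after background pregabalin or gabapentin is stopped, so off-drug scores that SAP 2.5.2 excludes can stay in the primary analysis

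*SAP*

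**What the plan says.** The rule is in SAP 2.5.2, in the same terms as Protocol 9.4.2: "Efficacy observations collected during the period of changes in doses of concomitant medication for PHN (compared to baseline) and the 2-days thereafter will be excluded". The resulting gaps are multiply imputed under MAR. The comparison is with the baseline dose, so the exclusion should last as long as the dose differs from it.

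The derivation is in SAP 5.1.5, in three steps.

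- Identification is deferred: "Programming Dataset Specification (PDS) will describe how to identify dose changes of concomitant PHN medications and prohibited medications".
- The end of the window is fixed in the SAP itself: "determine exclusion period: CM end date + x days". The tail x is 3 days for dose changes and 7 days for prohibited medication.
- A fallback covers open records: "if no medication end date available, then all values from medication start date onwards should be excluded".

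Section 5.1.5 gives a start for the window only in the fallback, and does not mention a drug that is stopped.

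Protocol 5.5.7 allows one of pregabalin or gabapentin, which "must remain at stable doses throughout the study". It asks sites to record medications that are administered. Table 2-1 of the SAP covers a change of drug: "Any change to a different standard of care medication from baseline (e.g. switch from pregabalin to gabapentin) will be treated as prohibited medication". Neither document names stopping the background drug without replacement as an event.

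**The concern.** A dose of zero differs from the baseline dose, so under 2.5.2 every score after a stop is excluded until the drug is resumed. Under 5.1.5 the window is tied to a medication end date. A reduced or increased dose entered as a new record has an end date that closes the changed period, or no end date, in which case everything from its start is removed. Either way the window covers the deviation. A plain stop creates no new record, because nothing is being administered. The only end date is that of the baseline-dose record, and it falls at the beginning of the deviation instead of its end.

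At stake is whether Week 12 scores taken without the baseline analgesic enter the primary ANCOVA as unaffected. The same handling carries into the MAR supplementary analysis (SAP 2.5.4.1), the mFAS sensitivity analysis (2.5.4.2) and the responder analysis (2.7.2). SAP section 4 drops the third supplementary analysis, which disregarded PHN dose changes and could have shown how much this handling matters.

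**Working it through.** The plan states no figure that depends on this window, so there is none to reproduce. The check counts days under the two rules.

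Inputs:

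- Tail x = 3 days for dose changes (SAP 5.1.5), against 2 days in SAP 2.5.2.
- Minimum data for a weekly mean: one daily score (SAP 2.5.3).
- Treatment epoch of 12 weeks, taken as diary days 1 to 84, with Week 12 as days 78 to 84 (assumed).
- Last background dose on day s, no replacement, not resumed, patient still on study treatment.
- End date of the only medication record = s.

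Formulas:

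- Off-drug days = 84 − s.
- Off-drug days excluded by 5.1.5 = 3 (days s + 1 to s + 3).
- Off-drug days kept by 5.1.5 = 84 − s − 3.
- Off-drug days kept by 2.5.2 = 0, because the dose never returns to baseline.

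| Last dose, day s | Off-drug days | Excluded by 5.1.5 | Kept by 5.1.5 | Off-drug Week 12 scores kept by 5.1.5 | Kept by 2.5.2 |
|---|---|---|---|---|---|
| 7 | 77 | 3 | 74 | 7 of 7 | 0 |
| 28 | 56 | 3 | 53 | 7 of 7 | 0 |
| 56 | 28 | 3 | 25 | 7 of 7 | 0 |
| 70 | 14 | 3 | 11 | 7 of 7 | 0 |
| 77 | 7 | 3 | 4 | 4 of 7 | 0 |
| 80 | 4 | 3 | 1 | 1 of 4 | 0 |

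All seven Week 12 scores survive whenever s + 3 < 78, that is, for any stop up to day 74. Even the single off-drug score left after a stop on day 80 enters the weekly mean.

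The tail is not the cause. With x = 2 counted from the same end date, a stop on day 28 keeps 84 − 28 − 2 = 54 of 56 days instead of 53. The anchor drives the result. The 2-versus-3-day difference is a separate inconsistency in the same line.

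How many patients this could reach is not in the documents. Only users of pregabalin or gabapentin can stop it. If 30% to 50% of the 129 randomized patients are users and 2% to 5% of users stop before Week 12 (both ranges assumed), the count runs from 0.30 × 0.02 × 129 = 0.8 to 0.50 × 0.05 × 129 = 3.2, or about 1 to 3 patients in total. With about 129 / 3 = 43 per arm, each patient shifts the crude arm mean by 1/43 = 0.02 points for every NRS point between the retained score and its MAR-imputed replacement. Three such patients in one arm would shift it by 3/43 = 0.07 per point. These are illustrations, not estimates.

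**The case against.** The strongest reply is that 5.1.5 is only a derivation note to 2.5.2, and a programmer who holds both has the right rule. SAP 2.7.2 repeats that a completer whose Week 12 value is affected by a PHN dose change is imputed under MAR. The PDS decides what counts as a dose change, and it may code a stop as a zero-dose period with no end date. The fallback for open records would then exclude everything from the stop onwards. This stands as far as it goes: the documents neither confirm nor rule out such coding, so the misuse of scores is not established as an outcome. It does not remove the conflict. What is deferred to the PDS is how dose changes are identified. The formula for the end of the window is fixed in the SAP, and applied to a stop it contradicts 2.5.2.

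A reader might go further and infer that 5.1.5 deletes the stable-dose scores and keeps only the off-drug ones, by opening the window at the start of the baseline-dose record. The text does not support that. If the bullets applied to baseline-dose records, the fallback would also delete every score of every patient on ongoing, stable pregabalin or gabapentin, which cannot be intended.

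It is also fair that much lies outside the problem. A switch of drug is prohibited medication. A dose change with its own record is handled correctly. Scores after stopping study treatment for anything but an adverse event, lack of efficacy or prohibited medication, including the urgent safety measures, are excluded and imputed under MAR in any case. SAP Amendment 1 says there were many discontinuations due to the termination, so fewer patients have an on-treatment Week 12 score that could be mishandled.

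**Conclusion.** The point holds as a conflict between two sections of the SAP, confined to patients who stop background pregabalin or gabapentin without replacement while still on study treatment. For them the end-date formula keeps nearly all later off-drug scores, and all of Week 12 for stops up to day 74, where 2.5.2 and Protocol 9.4.2 keep none. This assumes that the stop is recorded only as the end date of the baseline-dose record and that the PDS does not code it as an open-ended change.

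Two stronger conclusions are tempting and not supported. One is that all off-drug scores certainly enter the primary analysis: the first three days are excluded even on the literal reading, and the PDS has not been seen. The other is that the treatment comparison is biased, or biased differently by arm. Stopping background drug may well be related to response or tolerability, but the documents give neither the number of users nor the number who stopped, so size and direction are unknown. With only background-drug users at risk, the effect is probably small. The correction is still worth making, because it is cheap and removes a contradiction in the primary analysis.

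**What to change.** In SAP 5.1.5, define the analysis window from the deviation instead of from a record's end date:

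- Open it on the first day the PHN dose differs from the baseline dose, whether increased, decreased or zero.
- Close it on the day the baseline dose is resumed plus a single tail, after reconciling the 2 days of SAP 2.5.2 and Protocol 9.4.2 with the 3 days of 5.1.5.
- If the baseline dose is not resumed, run the window through Week 12.
- Impute the excluded scores under MAR, as 2.5.2 already provides.

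Align the PDS with this rule, including how a stop is flagged. If the PDS already treats a stop as an open-ended change, say so in 5.1.5. The cost is a short addition to the SAP and a check of the derivation before database lock. It restates the rule in 2.5.2, so the estimand does not change and no new data are needed.
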